APPENDIX III: VISUAL ACUITY ASSESSMENT

Visual acuity will be measured by the M&S Technologies Smart System II (Park Ridge, IL). This is a computer generated visual acuity test. The Smart System II comprises a computer processor, using a flat LCD screen monitor, and an interactive keypad controller. The LCD screen monitor is wall-mounted and manufactured to M&S Technologies' specifications, with high resolution and a 450:1 nominal contrast ratio. The examiner uses the keypad to access directly each primary acuity test, specific optotypes, randomization options, and to increase or decrease the size of the optotype on demand. The system allows the examiner to present random letter sequences to preclude subjects from memorizing the sequence to pass each line. The Smart System II can be calibrated for lane lengths of 6 to 22 feet.

APPENDIX IV: BIOMICROSCOPY/EXTERNAL EYE EXAMINATION

Slit lamp biomicroscopy will be performed and the observations will be graded as described below:

Lashes

0= Normal
1= Abnormal

Eyelid

Erythema

0 = Normal, without any redness
+1 = A low grade flushed reddish color
+2 = Diffused redness encompassing the entire lid margin
+3 = Deep diffused reddish color of lid margins and superior or inferior eyelid

Edema

0 = Normal, no swelling of the lid tissue
+1 = Slight diffuse swelling above normal
+2 = General swelling
+3 = Swelling sufficient to close the lid

Conjunctiva

Erythema

0 = Normal
+1 = A flush, pink color predominantly confined to the palpebral or bulbar conjunctiva; slight localized injection
+2 = More prominent red color of the palpebral or bulbar conjunctiva
+3 = Marked redness of the palpebral or bulbar conjunctiva

Edema

0 = Normal, no swelling of the conjunctiva
+1 = Slight diffuse or regional swelling of the conjunctiva
+2 = General swelling of the conjunctiva
+3 = Extensive swelling of the conjunctiva

Tear Film Debris

0 = None; absence of debris
+1 = Mild; presence of debris in inferior tear meniscus
+2 = Moderate; presence of debris in inferior tear meniscus and in tear film overlying cornea
+3 = Severe; presence of debris in inferior tear meniscus and in tear film overlying cornea
presence of mucus strands in inferior fornix or on bulbar conjunctiva
+4 = Very Severe; presence of debris in inferior tear meniscus and in tear film overlying cornea;
presence of numerous AND/OR adherent mucus strands in inferior fornix and on bulbar conjunctiva or filamentary keratitis

Cornea

Endothelial Changes

- 0 = Normal
- +1 = Slight pigment, keratoprecipitates, guttata
- +2 = Moderate pigment, keratoprecipitates, guttata
- +3 = Dense pigment, keratoprecipitates, guttata

Edema

- 0 = None, transparent and clear
- +1 = Mild, dull glassy appearance
- +2 = Moderate, dull glassy appearance of epithelium with large number of vacuoles
- +3 = Severe, epithelial bullae and/or stromal edema, localized or diffuse, with or without stromal striae.

Anterior Chamber

Cells

- 0 = No cells seen
- +1 = + cells
- +2 = ++ cells
- +3 = +++ cells
- +4 = +++++ cells, Hypopyon formation

Flare

- 0 = No Tyndall effect
- +1 = Tyndall beam in the anterior chamber has a mild intensity
- +2 = Tyndall beam in the anterior chamber is of strong intensity
- +3 = Tyndall beam is very intense; the aqueous has a white, milky appearance

Lens Pathology

- 0 = Normal; no opacity in the lens
- 1 = Abnormal; existing opacity in the lens; aphakic or pseudophakic eyes or other abnormal findings.

APPENDIX V: FLUORESCEIN TEAR BREAK-UP TIME (TBUT)

Non-preserved fluorescein will be used to conduct this assessment. When conducting all assessments room temperature and humidity should be relatively consistent throughout each visit and throughout the study.

TBUT should be conducted as specified in [Appendix I: Schedule of Visits and Procedures](#).

Fluorescein Tear Break-Up Time

- Perform the examination with the slit lamp at 10X magnification and cobalt blue illumination.
- Draw 5 μ L of 2% sodium fluorescein into the micropipette, allowing a drop to form.
- Gently touch the drop at the tip of the delivery dropper to the lower palpebral conjunctiva of the right eye.
- In order to thoroughly mix the fluorescein with the tear film, ask the subject to blink several times and move his/her eye around.
- Using a stop watch, measure the time it takes for the appearance of the first dry spot after blinking.
- Ask the subject to blink again and repeat the measurement of the time it takes for the appearance of the first dry spot after blinking. Repeat this procedure once more for a total of three measurements.

NOTE: If this procedure is completed within two minutes, proceed to measure corneal staining in the same eye as described in [Appendix VI](#) without applying more fluorescein.

- Repeat these steps for the left eye.
- Using these three assessments calculate the mean time in seconds for each eye and record this time in the subject's chart as well as the case report form.

[figure not shown]
APPENDIX VI: FLUORESCEIN CORNEAL STAINING

The cornea will be stained with non-preserved, 2% fluorescein as described by Lemp et al. (Lemp, 1995). When conducting all assessments room temperature and humidity should be relatively consistent throughout each visit and throughout the study.

Corneal Staining should be conducted as specified in Appendix I: Schedule of Visits and Procedures.

Corneal Staining

- Using a yellow barrier filter (Wratten or Tiffen #11 or #12) and the slit lamp with cobalt blue illumination, with a 3 mm slit width and 10X or 16X magnification.
- Draw a 5 μ L drop of fluorescein in the right eye.
- In order to thoroughly mix the fluorescein with the tear film, ask the subject to blink several times and move his/her eye around.
- Wait two minutes.
- Evaluate the cornea for staining referencing the diagram below.
- Punctate staining is recorded using a standard grading system of 0-3 for each of the five areas shown below.
- Repeat this procedure for the left eye.

[figure not shown]

APPENDIX VII: LISSAMINE GREEN CONJUNCTIVAL STAINING

The conjunctiva will be stained with non-preserved, 1% lissamine green as described by Lemp et al. (Lemp, 1995). When conducting all assessments room temperature and humidity should be relatively consistent throughout each visit and throughout the study.

Conjunctival Staining should be conducted as specified in Appendix I: Schedule of Visits and Procedures.

- Without flushing the eye from the previous assessment, instill a 20 μ l drop of lissamine green to the right eye using a micropipette, allowing a drop to form.
- Gently touch the drop at the tip of the delivery dropper to the lower palpebral conjunctiva of the right eye.
- In order to thoroughly coat the ocular surface with the lissamine, ask the subject to blink several times and move his/her eye around.
- After 1 minute and before 4 minutes have elapsed, using white light of moderate intensity, grade the areas of the conjunctiva of the right eye with the 0-3 scale shown below.
- Repeat this procedure for the left eye.

APPENDIX VIII: INSTILLATION OF MEDICATION

Study personnel will instill medication at Visit 2 (First Treatment Visit) and Visit 3 (Second Treatment Visit).

Instilling the Medication

- The study personnel will remove the study medication from the refrigerator at least 15 minutes prior to planned administration.
- The study personnel will record the kit number in the subject's records and the Subject ID number on the labels of the kit and vial pouches before proceeding with dosing the subject:
- Confirm that the visit number on the pouch corresponds to the subject's visit
- Open the pouch
- Instruct subject to slightly tilt his/her head back and look upward
- The study personnel should gently squeeze the bottle allowing one drop to coat the ocular surface.
- Repeat procedure for left eye using the same bottle.
- The subject should gently close his or her eyes for a few seconds.
- Use one pouch of assigned study medication for Visit 2 and one pouch for Visit 3.
- The used bottle should be returned to its pouch and the pouch returned to its kit box.
- After dose administration at Visit 2, return the kit containing one used, and one unused bottle to the refrigerator.
- After dosing at Visit 3, return the bottle into the pouch and place the pouch in the kit box. At this time, the kit containing two used bottles can be stored at room temperature before returning to the sponsor for disposal.

APPENDIX IX: DRY EYE SYMPTOM QUESTIONNAIRES

The following subject reported outcomes measurements will be collected as noted in [Appendix I](#):

- SANDE
- SPEED
- OSDI

SYMPTOM ASSESSMENT IN DRY EYE QUESTIONNAIRE (SANDE) ([Schaumberg, 2007](#))

Part 1 (administer at Visits 1, 2, and 3)

PLEASE COMPLETE THE FOLLOWING QUESTIONS REGARDING THE FREQUENCY AND SEVERITY OF YOUR DRY EYE SYMPTOMS

1. Frequency of symptoms:

Please place an 'I' on the line to indicate how often, on average, your eyes felt **dry and/or irritated** in the past day:

Rarely ————— **All the time**

2. Severity of symptoms:

Please place an 'I' on the line to indicate how severe, on average, you feel your symptoms of **dryness and /or irritation** were in the past day:

Very Mild ————— **Very Severe**

Part 2 (administer at only Visits 2 and 3)

PLEASE COMPLETE THE FOLLOWING QUESTIONS REGARDING THE FREQUENCY AND SEVERITY OF YOUR DRY EYE SYMPTOMS

1. Frequency of symptoms:

Please place an 'I' on the line to indicate how often, on average, your eyes feel dry or irritated now compared to at your last visit

2. Severity of symptoms:

Please place an 'I' on the line to indicate how severe, on average, you feel your symptoms of dryness and irritation are now compared to at your last visit

SPEED QUESTIONNAIRE (Ngo, 2013 and Korb, 2005)

1. Report the type of SYMPTOMS you experience and when they occur:

Symptoms	At this Visit		Within the past 72 hours		Within past 3 months	
	Yes	No	Yes	No	Yes	No
Dryness						
Grittiness or Scratchiness						
Soreness or Irritation						
Burning or Watering						
Fatigue						

2. Report the FREQUENCY of your symptoms using the rating list below:

Symptoms	0	1	2	3
Dryness				
Grittiness or Scratchiness				
Soreness or Irritation				
Burning or Watering				
Fatigue				

0 = Never

1 = Sometimes

2 = Often

3 = Constant

3. Report the FREQUENCY of your symptoms using the rating list below:

Symptoms	0	1	2	3	4
Dryness					
Grittiness or Scratchiness					
Soreness or Irritation					
Burning or Watering					
Fatigue					

0 = No problems

1 = Tolerable; not perfect, but not uncomfortable

2 = Uncomfortable; irritating, but does not interfere with my day

3 = Bothersome; irritating and interferes with my day

4 = Intolerable; unable to perform my daily tasks

OCULAR SYMPTOM DISEASE INDEX (Schiffman, 2000)

Please answer the questions by checking the box that best represents your answer

HAVE YOU EXPERIENCED ANY OF THE FOLLOWING DURING THE LAST WEEK:

	All of the time	Most of the time	Half of the time	Some of the time	None of the time
1. Eyes that are sensitive to light?	4	3	2	1	0
2. Eyes that feel gritty?	4	3	2	1	0
3. Painful or sore eyes?	4	3	2	1	0
4. Blurred vision?	4	3	2	1	0
5. Poor vision?	4	3	2	1	0

HAVE PROBLEMS WITH YOUR EYES LIMITED YOU IN PERFORMING ANY OF THE FOLLOWING DURING THE LAST WEEK:

	All of the time	Most of the time	Half of the time	Some of the time	None of the time	N/A
6. Reading?	4	3	2	1	0	N/A
7. Driving at night?	4	3	2	1	0	N/A
8. Working with a computer or bank machine (ATM)?	4	3	2	1	0	N/A
9. Watching TV?	4	3	2	1	0	N/A

HAVE YOUR EYES FELT UNCOMFORTABLE IN ANY OF THE FOLLOWING SITUATIONS DURING THE LAST WEEK:

	All of the time	Most of the time	Half of the time	Some of the time	None of the time	N/A
10. Windy conditions?	4	3	2	1	0	N/A
11. Places or areas with low humidity (very dry)?	4	3	2	1	0	N/A
12. Areas that are air conditioned?	4	3	2	1	0	N/A

APPENDIX X: TEAR VOLUME ASSESSMENTS:

Three assessments of tear volume are used in the study: Ultra high resolution optical coherence tomography (UHR-OCT) measuring tear volume and tear meniscus height, lower tear meniscus height measured by Keratograph 5M, and Schirmer's test. The sections below briefly describe procedures for each.

Tear meniscus imaged Ultra High Resolution Optical Coherence Tomography (UHR-OCT)

The custom-built ultra-high resolution (3 microns axial resolution) spectral domain OCT can image a full 15mm width scan at up to 48 images per second. The tear meniscus around the upper and lower eyelids can be imaged and measured with the OCT, a unique capability. The OCT images obtained with this system show the tear menisci around both eyelids ([Figure 1](#)).

Figure 1: Tear menisci imaged with UHR-OCT

[figure not shown]

Figure 1: Upper and lower tear menisci imaged with ultra-high resolution optical coherence tomography. A custom built 3 μm resolution ultra-high resolution optical coherence tomography was used to image both upper and lower tear menisci. The boundaries of the tear meniscus were clearly visualized. The bars denote to 500 μm .

[figure not shown]
OCT imaging

Each subject will be asked to sit in front of a slit-lamp, on which an OCT probe is mounted. An internal fixation target will be provided to facilitate the subject to keep the eye on a straight forward direction. The central OCT beam as indicated as a green line on the OCT monitor is set to be on the corneal apex ([Figure 1](#)), which a specular reflection is normally detected. Immediately after eye opening, corneal images with the OCT will be recorded. A vertical OCT scan with a scan width of up to 13 mm will be used so that the entire cornea and both upper and lower eyelids will be imaged. The measurements will be acquired in one scan with 3 images in the same fashion. The first image will be processed for the measurement. If the first image is not good, the second or third image will be used. The measurements of the image analyzed will be collected in the CRF.

Image process to yield the results.

All meniscus variables of upper (**A**) and lower (**B**) tear menisci are measured with a custom software program with operator inputs (TDanalyer, ver. 1.0) ([Figure 2](#)). Touch points (*pink dots*) between two elements (eyelid, cornea, and tear meniscus) and a middle point (*green dot*) of the front edge of the tear meniscus are marked. After that, the software process the image, to yield the results. The three-point method is used to fit a circle to yield tear the meniscus height and area. Tear meniscus height and area of both upper and lower tear menisci will be used. In addition, the eye lid length will be photographed and measured to calculate tear meniscus volumes in both upper and lower tear menisci.

Figure 2: Measuring menisci variables with UHR-OCT

[figure not shown]

Tear Meniscus Height measured by Keratograph 5M

[figure not shown]
Evaluation of tear film volume will be assessed via tear meniscus height measurements using the Keratograph 5M. High resolution images of the lower tear meniscus from both eyes are obtained under infrared light as indicated in the Keratograph 5M user manual. Using integrated magnification and measurement tools, the tear meniscus height of the lower lid margin are estimated. Detailed description of the operation of the instrument and software is described in Keratograph 5M user manual provided by Oculus.

Instructions:

[figure not shown]
- Turn on the computer. After turning on the computer the operating system loads the Keratograph 5M program. If necessary click on the Keratograph 5M icon .
- Turn on the Keratograph 5M
- Enter Subject information in the Patient Data Management Page.

[figure not shown]
- In the "Patient" box on the top left, select [New]. The following screen will appear:

- Enter the patient's last name, first name, and date of birth and click [Save].
- Click [Keratograph] in the “Functions” box to transition from the Patient Data Management to the Keratograph Overview.
- In the “Examination” menu click [New] and the following screen will appear:

- Activate the **[Tear Meniscus Height]** function button on the “TF Scan” Box on the left.
- In the illumination box on the right-hand side of the screen, select **[IR]** lighting.
- If necessary, adjust the camera for optimal focusing on the tear meniscus as seen on the example in the image below (i.e. at approximately the 6:00 position).

- After a blink, focus the camera on the central part of the tear meniscus of the lower eyelid as indicated in the red circle above.
- Click on the **[Image]** button to record the image.
- The magnification changer and camera settings located at the right-hand side of the screen are set to optimal settings. No adjustments should be needed.
- Confirm that the image is in focus at the central area of the eyelid (below the center of the iris), if not, repeat the image.

Note: This procedure is repeated to obtain 3 quality images per eye

Repeat the procedure for the other eye.

[figure not shown]
- Select [Close] after the three images have been taken.

Measurement of the Tear Meniscus Height (TMH)

- From the three images from each eye obtained above, the tear meniscus height is measured with a software-integrated ruler. The evaluations can be made at different magnification levels. Select a higher magnification if necessary.

[figure not shown]
If the TMH is not measured at the time the image is captured, select the patient and the assessment from the Patient Data Management Page by double clicking on the assessment on the right of the screen for the selected patient on the left.

The following screen will be displayed:

- Measure the tear meniscus height with the ruler option.
- Select the following button  from the left of the screen with the left mouse button.

- The button will be highlighted in blue.
- Click once with the left mouse button on the edge of the lower eyelid to position one of the edges of the measurement.
- Move the cursor vertically from this edge to the upper tear meniscus margin and click the left mouse button again.
- The measurement length will appear on the image (in millimeters) as indicated below:

- The system will display the real measurement regardless of the magnification used for the measurement.
- If the selection of the tear meniscus height is not accurate, delete the measurement and repeat the procedure.
- Record the distance of the TMH.
- Repeat the procedure for the all three images of each eye.
- Click [Close] and the image with the measurement will be saved in the patient file.

Schirmer's Test

Schirmer's strips will be supplied to the clinical site. When conducting assessments room temperature and humidity should be relatively consistent throughout each visit and throughout the study.

Schirmer's Test without Anesthesia

- While still in the plastic sheath, fold the notched end of the Schirmer at the apex of "v". Additionally, fold a partial second fold at the halfway point of the strip so that the strip does not lie directly in the subject's line of sight.
- Remove the right eye strip from the sheath.

- Ask the subject to look up and gently draw the right lower lid in a downward and temporal direction.
- Place the rounded end of the strip toward the temporal one-third of the lower eyelid.
- Repeat this procedure in the left eye.
- Darken slightly the room, and instruct the subject to relax and look at an object in the room while blinking normally or have subjects gently close eyes.
- Strips are removed after five minutes.
- After removing the strips, with a sharp pencil draw a horizontal line across the leading edge of moisture and a second horizontal line across the lowest point of moisture.
- Using a ruler and/or the millimeters recorded on the strips, measure a point halfway between the two lines and record this as the amount of wetting.

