4.2.2 Secondary Endpoints

The secondary endpoints are to:

- assess changes in lower tear meniscus height by Keratograph 5M
- compare lower tear meniscus height measurements between UHR-OCT and Keratograph 5M

- assess the duration of action of P-321 Ophthalmic Solution
- compare the pharmacodynamic activity of different strengths of P-321 in subjects with tear-deficient dry eye
- monitor safety and tolerability of P-321 Ophthalmic Solution

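### Three UHR-OCT images are taken per scan but only one is measured, so the primary readings at Visits 2 and 3 carry some noise that averaging the existing images would reduce

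*Combined protocol and SAP*

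**What the plan says.** Section 4.2.1 makes UHR-OCT the instrument for the primary endpoint. On acquisition, Appendix X says "The measurements will be acquired in one scan with 3 images in the same fashion". On reading, it says "The first image will be processed for the measurement. If the first image is not good, the second or third image will be used", and then "The measurements of the image analyzed will be collected in the CRF". The meniscus variables "are measured with a custom software program with operator inputs": contact points and a middle point are marked on the image and a circle is fitted through them. Appendix X gives no criterion for rejecting an image, does not name who decides, and provides for no repeat reading and no averaging across the three images.

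For the Keratograph 5M, Appendix X asks for three good images per eye and a height measurement on each: "Repeat the procedure for the all three images of each eye". It does not say how the three heights are combined. Section 4.2.2 lists, among the secondary endpoints, to "compare lower tear meniscus height measurements between UHR-OCT and Keratograph 5M".

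The only OCT averaging that the protocol describes is in Section 4.1, over three time points at Visit 1. At Visits 2 and 3 there is one pre-dose reading and six post-dose readings per eye (Sections 6.2 and 6.3), each from one image. Appendix X gives the same reading rule in both protocol versions in the file.

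**The concern.** Whatever error arises from marking points by hand on one frame goes undiluted into every primary reading at the treatment visits. The images that could reduce it are already acquired, so the loss is avoidable without asking more of the subject. The trial is small: about 24 subjects, with a dose decision after about 8 (Section 6.5) and each dose compared with placebo (Section 8.1.2). If the Phase 2 dose differs from 0.017%, those comparisons rest on about 8 and 24 - 8 = 16 subjects. What is at stake is precision, and also a record of within-scan repeatability, which the present rule cannot provide because only one image per scan reaches the CRF.

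**Working it through.** **Inputs.** From Section 8.2: N = 24, 2x2 crossover, difference 60 µm, within-subject SD stated as 71 µm, power stated as 98% at 1 hour. From Section 8.3: alpha 0.05, taken here as two-sided because sidedness is not stated. From Appendix X: three images per scan, one measured. *Assumed:* r, the share of the variance behind the 71 µm that is per-image error. The documents give no figure for it, so a range is shown.

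**The plan's own figure.** Noncentral t, 22 df:

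- (a) 71 as the SD of the treatment difference: SE = 71/√24 = 14.49, ncp = 60/14.49 = 4.14, power 97.7% (98.5% by the normal approximation). This reproduces 98%.
- (b) 71 as a true within-subject SD: SE = 71 × √(2/24) = 20.50, ncp = 60/20.50 = 2.93, power 79.9% (83.3% by the normal approximation). This does not.
- Counting 48 eyes as independent under (b) gives 98.2%, which also matches 98%.

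The label in Section 8.2 fits (b) and the stated power fits (a), so both are carried forward.

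**Effect of averaging three images.** Independent per-image error variance falls by two thirds, so the total variance is multiplied by 1 - 2r/3 and the SD becomes 71 × √(1 - 2r/3).

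| Assumed r | SD (µm) | Power, (a), N = 24 | Power, (b), N = 24 |
|---|---|---|---|
| 0 (one image) | 71.0 | 97.7% | 79.9% |
| 5% | 69.8 | 98.0% | 81.2% |
| 10% | 68.6 | 98.4% | 82.5% |
| 20% | 66.1 | 98.9% | 85.2% |
| 30% | 63.5 | 99.3% | 87.8% |

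The gain for r from 5% to 30% is about 0.3 to 1.6 points under (a) and about 1.3 to 8 points under (b).

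**Dose-level subsets** (power at r = 0, 10%, 30%):

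| N | (a) | (b) |
|---|---|---|
| 16 | 88.1%, 90.2%, 93.9% | 60.4%, 63.4%, 70.1% |
| 8 | 51.8%, 54.5%, 60.9% | 29.7%, 31.4%, 35.6% |

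In absolute points the gain exceeds that at N = 24 for both subsets under (a). Under (b) this is so at N = 16 but not at N = 8.

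**A small error.** An assumed per-image error SD of 10 µm is a share of 10²/71² = 2% under (b), or 10²/(71²/2) = 4% under (a). The gain at N = 24 is then below 1 point on either reading.

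**Correlated errors.** If per-image errors within a scan have correlation ρ, the variance removed is (2/3) × r × (1 - ρ). With r = 30% and an assumed ρ = 0.5 that is 10% of the total, the same as an independent share of 15%, so the gain falls between the 10% and 20% rows.

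**Marking load.** 24 subjects × 2 eyes × (3 + 7 + 7) time points = 816 images now; × 3 = 2,448 if all are gradable. With an upper and a lower meniscus on each, the fits rise from 1,632 to 4,896.

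**The case against.** The strongest reply is that the gain may be negligible. The device "can image a full 15mm width scan at up to 48 images per second", so three consecutive frames would span about 3/48 = 1/16 of a second (the actual spacing is not stated). Averaging such frames removes marking and frame noise only. It leaves an operator's consistent placement habit and the variation between time points and days, which may dominate the 71 µm. Some averaging also exists already: over time points at Visit 1, and over post-dose readings in the six-hour average and the exploratory AUC. All of this stands, and it limits the size of the point. It does not remove it, because individual time-point readings at Visits 2 and 3 still rest on one image.

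A reader might go further in three ways that the documents do not support:

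- *That the choice of image biases the treatment comparison.* The rule is fixed: the first image is used unless it is unsatisfactory. It turns on the image, not on the value obtained. Section 7.1 has site personnel masked, and although the Data Review Group sees unmasked data, nothing says that its members grade images. With masked reading this is noise. The lack of a written criterion is a gap to close, not evidence of bias.
- *That the secondary instrument has the more precise procedure, and that averaging both would make them comparable.* No precision is given for either device, and the combination of the Keratograph readings is undefined. The Keratograph images are separate captures, each after a blink and focusing, whereas the OCT images come from one scan. Random single-image error does not shift the mean difference between devices.
- *That power would rise from about 80% to well above it.* That holds only under reading (b), with large and independent image errors.

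**Conclusion.** The point holds as a low-cost improvement in precision. One operator-marked image is measured out of three acquired, and averaging would reduce whatever independent marking and frame noise it carries. How much that is worth cannot be derived from the documents. Under the reading of the SD that reproduces the stated power, the benefit at 24 subjects is under 2 points for assumed shares up to 30%. Under the literal reading of the label it could reach about 8 points. Both ranges describe a single-time-point comparison and assume independent errors; correlation within a scan lowers them. The point neither identifies a bias nor undermines the primary analysis, and the change would not make the two instruments fully comparable.

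**What to change.** In the OCT part of Appendix X, replace the one-image rule with three steps:

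1. Decide whether each of the three images is gradable before any point is placed, from written image features only (for example, all contact points visible and no blink).
2. Measure every gradable image.
3. Record in the CRF the mean per eye and time point for LTMH, UTMH and the areas used for volume, with the individual readings and the number of images used.

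In the Keratograph part, state that the mean of the three readings is the value analysed.

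No new imaging or subject time is needed. The cost is reading time: up to 2,448 images instead of 816, each with an upper and a lower meniscus to fit, which can be done offline. The retained readings would also give the trial's own estimate of within-scan repeatability.
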